3.6. End of Study

End of study is defined as when the last subject has completed 4 weeks of study treatment and the FU visit approximately 28 days after the last dose of study drug, as applicable.

3.7. Poststudy Care

The long-term care of subjects poststudy will remain the responsibility of their primary treating physician.

3.8. Biomarker Testing

3.8.1. Biomarker Samples to Address the Study Objectives

The biomarker sample collection schedule is described in the Study Procedures Table ([Appendix 3](#)). Samples will be collected from all subjects. The biomarker samples will be destroyed no later than 15 years after the end of study or per country requirements.

3.8.2. Biomarker Samples for Optional Future Research

CCI [REDACTED]

[REDACTED]

[REDACTED]

[REDACTED]

3.8.3. Biomarker Samples for Optional Genomic Research

CCI [REDACTED]

[REDACTED]

[REDACTED]

3.8.4. Sample Storage

The stored biological samples may be used by Gilead or its research partner for future testing to provide additional data to answer questions that relate to the main study. At the end of this study, these samples may be retained in storage by Gilead for a period up to 15 years. If subjects provide additional specific consent, residual PK samples may be destroyed no later than 15 years after the end of study or per country requirements.

4. SUBJECT POPULATION

4.1. Number of Subjects and Subject Selection

A sufficient number of subjects will be screened to enroll approximately 12 evaluable subjects with active ACLE or SCLE.

4.1.1. Subject Replacement

Subjects who permanently discontinue study drug before the end of study treatment may be replaced.

Criteria for subject replacement by the sponsor include but are not limited to the following circumstances:

- Study drug discontinuation prior to the PK sampling visit
- Study drug discontinuation due to an AE categorized as not related to study treatment by the investigator
- Study drug discontinuation due to subject request or subject noncompliance
- Study drug interruption > 3 days
- Use of prohibited concomitant medication or modification of background standard of care medication

4.2. Inclusion Criteria

Subjects must meet **all** of the following inclusion criteria to be eligible for participation in this study.

Documentation of select criteria (*) **must** be submitted to the study sponsor for review and confirmation of subject eligibility prior to randomization:

- 1) Are ≥ 18 and ≤ 75 years of age at the time of the initial informed consent
- 2) Either fulfill EULAR/ACR 2019 classification criteria for SLE*
or
have biopsy-proven CLE*
- 3) Must have active ACLE/SCLE* {[Klein 2010](#)}; subjects with mixed skin presentations of lupus skin disease (including DLE) are allowed to enter

- 4) CLASI activity score^a of ≥ 6 during screening* and Day 1

^aExcluding the alopecia component (ie, points for recent hair loss and alopecia do not contribute to the qualifying CLASI-A score)
- 5) Presence of at least 1 representative lupus skin lesion amenable to punch biopsy and subject willingness to undergo skin biopsy at 2 time points
- 6) Subjects using protocol-permitted nonbiologic immunosuppressive/immunomodulatory agents for the treatment of CLE/SLE (eg, antimalarials, MTX, or other csDMARDs) must maintain stable dose(s) for ≥ 60 days prior to randomization through Week 4 of the study (see Section 5.4.1 for details)
- 7) Subjects using protocol-permitted Class V-VII topical corticosteroids or oral prednisone ≤ 15 mg/day (or equivalent) must maintain stable dose(s) for ≥ 28 days prior to randomization through Week 4 of the study (see Section 5.4.1)
- 8) Must have prior intolerance or inadequate response at any time (per investigator judgment) to at least one of the following medications for the treatment of SLE/CLE:
 - a) Topical corticosteroids or topical calcineurin inhibitors
 - b) Oral corticosteroids
 - c) A csDMARD, including, but not limited to: chloroquine, quinacrine, hydroxychloroquine, azathioprine, MMF, leflunomide, dapsone, or MTX
- 9) Must have a body mass index (BMI) between 18 and 35 kg/m²
- 10) Subjects of childbearing potential who engage in heterosexual intercourse must agree to use protocol-specified method(s) of contraception as described in [Appendix 4](#)
- 11) Able and willing to sign the informed consent form(s) (ICF), as approved by the IRB/IEC; written, signed, and dated consent must be provided before initiating any screening evaluation

4.3. Exclusion Criteria

Subjects who meet any of the following exclusion criteria are not eligible to be enrolled in this study.

Consultation with the sponsor medical monitor on select criteria (*) must take place prior to randomization.

- 1) Present with only CCLE skin lesion(s) during screening and Day 1

- 2) Have highly active SLE (including but not limited to lupus nephritis, neuropsychiatric SLE, vasculitis) that could put the subject at risk per the investigator's judgment
- 3) Presence of active skin conditions other than cutaneous lupus that may interfere with assessing lupus-specific skin lesion(s) (eg, lupus-nonspecific skin disease, psoriasis, drug-induced lupus)
- 4) Meet any of the following prior/concomitant medication use criteria relative to the date of randomization:
 - a) Prior use of an IRAK4 inhibitor at any time
 - b) Exposure to any approved or investigational bDMARD within 180 days
 - c) Exposure to cyclophosphamide within 60 days
 - d) Exposure to a JAK inhibitor (eg, tofacitinib, baricitinib, upadacitinib) within 60 days
 - e) Use of oral prednisone > 15 mg/day (or equivalent) within 28 days
 - f) Use of Class I-IV topical corticosteroids within 28 days
 - g) Use of topical calcineurin inhibitors within 28 days
 - h) Use of injectable corticosteroids within 28 days
 - i) Use of strong CYP3A inhibitors or inducers within 14 days (see Section 5.4.2)
- 5) Meet any of the following infection criteria:
 - a) Any active infection that is clinically significant (per investigator judgment); baseline SARS-CoV-2 screening should follow local guidelines/institutional practice*
 - b) Positive QuantiFERON at screening; subjects with a positive test are excluded from the study and should be worked up as per local standard of care.

Note: QuantiFERON tests with inconclusive results may be repeated one time. If the repeat result is also inconclusive, the subject must be excluded from the study.

Note: Subjects with prior latent TB who have been treated with a full course of prophylaxis as per local guidelines are eligible. Appropriate documentation of prior treatment is required, a QuantiFERON test is not required.*
 - c) An infection requiring oral anti-infective medication(s) within 28 days prior to randomization

- d) An infection requiring hospitalization or treatment with intravenous anti-infective medication(s) within 60 days prior to randomization
 - e) Evidence of human immunodeficiency virus (HIV) infection and/or positive HIV antibodies at screening
 - f) Active or chronic or past hepatitis B virus infection (HBV), as evidenced by positivity for hepatitis B surface antigen (HBsAg) or HBV core antibody (regardless of HBV viral load) at screening
 - g) Evidence of active HCV infection. Subjects with positive HCV antibody (Ab) at screening, require reflex testing for HCV RNA. Subjects with positive HCV RNA viral load (VL) at screening will be excluded. Subjects with positive HCV Ab, but negative HCV RNA VL are eligible per investigator judgment, but require a retest at Week 4
 - h) History of previous life-threatening or opportunistic infection
- 6) Meet any of the following central laboratory confirmed abnormalities:
- a) Hemoglobin < 10.0 g/dL (International System of Units [SI]: < 100.0 g/L)
 - b) ANC < LLN
 - c) Lymphocyte count < 800 cells/mm³ (SI: < 0.8 × 10⁹ cells/L)
 - d) Platelet count < LLN
 - e) ALT or AST ≥ 1.5 × ULN
 - f) Total bilirubin > 1.0 × ULN
 - g) Estimated CL_{cr} < LLN based on the Cockcroft-Gault equation
- 7) Subjects who are pregnant, breastfeeding, or planning to become pregnant or breastfeed during the study or for 14 days after their last dose of study drug
- 8) Any condition or circumstances which may make a subject unlikely or unable to complete the study or comply with study procedures and requirements (per investigator judgment)
- 9) Major surgery (requiring regional block or general anesthesia) within 28 days prior to randomization or planned during the subject's study participation
- 10) Known hypersensitivity to the study drug, its metabolites, or formulation excipients
- 11) Subject has presence or sequelae of gastrointestinal, liver, or other conditions known to interfere with the absorption, distribution, metabolism, or excretion of drugs; this may include a history of weight loss surgery

- 12) Subject concurrently participates or participated in a drug or drug/device investigational research study within 28 days or 5 half-lives of the investigational product, whichever is longer, prior to randomization
- 13) Subject has a history of malignancy within the past 5 years prior to screening with the exception of excised and curatively treated nonmetastatic basal cell carcinoma or squamous cell carcinoma of the skin or carcinoma in situ of cervix which is considered cured with minimal risk of recurrence
- 14) History of any lymphoproliferative disease
- 15) History of organ or bone marrow transplant
- 16) Receipt of any live/attenuated vaccine within 28 days prior to randomization or planned during the study or for 28 days after the subject's last dose of study drug
- 17) Any screening ECG finding deemed clinically significant per investigator judgement

4.4. Screen Failures

Retesting of screening laboratory tests may be performed one time prior to screen-failing the subject, if the investigator deems that the initial value was inconsistent with the subject's previous results; due either to error (eg, a mishandled/hemolyzed sample), or to an extenuating circumstance which has since resolved.

Subjects who do not meet eligibility criteria for study entry ("screen failures") may be rescreened once. Written approval from the sponsor medical monitor must be obtained prior to rescreening.

At the time of rescreening, the individual must repeat the informed consent process, sign a new ICF, and repeat all necessary screening procedures. A new screening number will be assigned.

5. INVESTIGATIONAL MEDICINAL PRODUCTS

5.1. Randomization, Blinding, and Treatment Codes Access

An interactive response technology (IRT) will be used to manage subject randomization and treatment assignments. It is the responsibility of the investigator to ensure that the subject is eligible for the study prior to enrollment. Dosing assignments will be maintained in an investigator- and subject-blinded fashion within the IRT system until study-wide unblinding or emergency unblinding.

5.1.1. Randomization

At the time of initial informed consent, subjects will be assigned a screening number. On Day 1, subjects who meet all eligibility criteria will be randomized to a treatment arm as outlined in Section 3.3 and assigned a subject number.

Once a number has been assigned to a subject, it will not be reassigned to another subject. Replacement subjects will be assigned to the same treatment group as the discontinued subject to be replaced.

5.1.2. Blinding

Investigator, site personnel, site pharmacist(s), and randomized subjects will be blinded to treatment assignment.

Contract research organization personnel will be blinded to treatment assignment.

Gilead personnel will be unblinded and will not communicate unblinded information to blinded sites or subjects as specified in sponsor standard operating procedures (SOPs).

5.1.3. Procedures for Breaking Treatment Codes

In the event of a medical emergency where breaking the blind is required to provide medical care to the subject, the investigator may obtain treatment assignment directly from the IRT for that subject (IRT vendor may be contacted in the case of technology failure). Gilead recommends but does not require that the investigator contact the sponsor medical monitor before breaking the blind. Treatment assignment should remain blinded unless that knowledge is necessary to determine subject emergency medical care. The rationale for unblinding must be clearly explained in source documentation and in the IRT, along with the date on which the treatment assignment was obtained. If a subject's treatment assignment is unblinded, the sponsor must be immediately notified.

Investigator and subject blinding to study treatment is critical to the integrity of this clinical study. Therefore, if a subject's treatment assignment is disclosed to the investigator, the subject will have study treatment discontinued. All subjects will be followed until study completion unless consent to do so is specifically withdrawn by the subject.

5.2. Description and Handling of GS-5718

5.2.1. Formulation

GS-5718 tablets are available in 15-mg and 100-mg strengths. GS-5718, 15-mg, tablets are round, plain-faced, and film-coated orange. GS-5718, 100-mg, tablets are capsule-shaped, plain-faced, and film-coated orange. In addition to the active ingredient, GS-5718 tablets also contain the following excipients: microcrystalline cellulose, mannitol, crospovidone, fumaric acid, magnesium stearate, polyvinyl alcohol, polyethylene glycol, talc, titanium dioxide, FD&C Yellow #6, FD&C Yellow #5, and FD&C Blue #2.

Placebo tablets to match the GS-5718 tablets are available for blinding purposes. PTM GS-5718 tablets are identical in weight, shape, color, and appearance to corresponding GS-5718 tablets. PTM GS-5718 tablets contain lactose monohydrate, microcrystalline cellulose, croscarmellose sodium, magnesium stearate, polyvinyl alcohol, polyethylene glycol, talc, titanium dioxide, FD&C Yellow #6, FD&C Yellow #5, and FD&C Blue #2.

5.2.2. Packaging and Labeling

GS-5718 and PTM GS-5718 tablets are packaged in white, high-density polyethylene bottles. Each bottle contains 30 tablets, silica gel desiccant, and polyester packing material. Each bottle is capped with a white, continuous thread, child-resistant polypropylene screw cap fitted with an induction-sealed, aluminum-faced liner.

Study drug(s) to be distributed to centers in the United States (US) and other participating countries shall be labeled to meet applicable requirements of the US FDA, European Union (EU) Guideline to Good Manufacturing Practice - Annex 13 (Investigational Medicinal Products), and/or other local regulations.

5.2.3. Storage and Handling

GS-5718 and PTM GS-5718 tablets should be stored below 30 °C (86 °F). Storage conditions are specified on the label. Until dispensed to the subjects, all bottles of study drugs should be stored in a securely locked area, accessible only to authorized site personnel.

To ensure the stability of the study drug and to ensure proper product identification, study drugs should not be stored in a container other than the container in which they are supplied. Keep the bottle tightly closed to protect from moisture.

Consideration should be given to handling, preparation, and disposal through measures that minimize drug contact with the body. Appropriate precautions should be followed to avoid direct eye contact or exposure through inhalation when handling GS-5718 tablets.

5.3. Dosage and Administration of GS-5718

The study medication will consist of 115 mg GS-5718 administered as one 100 mg and one 15 mg tablet for oral administration, and PTM GS-5718 tablets for oral administration. Study drugs will be administered orally once daily with or without food, with the exception of the Week 4 visit (fasting lipids and intensive PK sampling). Each subject should be provided instructions to maintain approximately the same daily time of administration to ensure a similar dosing interval between study drug doses. Study staff should also counsel subjects of the importance of study drug compliance.

For the Week 4 visit, subjects will be instructed to attend the site under fasted conditions (defined as no food or drink, except water for 8 hours prior). Subjects will be instructed to refrain from taking the Week 4 dose at home and to bring their study drug to the site for dosing. Subjects will continue to fast until after collection of the 4-hour PK sample.

For missed dose(s) of study drug, subjects should be instructed to take the missed dose(s) as soon as possible during the same day. If the missed dose is not taken on the original day, subjects should be cautioned not to double the next dose with the missed dose of study drug under any circumstance. In those cases, the missed dose should be returned to the original study drug bottle.

Subjects must be instructed to return the original study drug bottle, including missed dose(s) to the investigator site at the Week 4 visit. If the subject does not return the bottle at this time, the subject must be instructed to do so during the FU visit.

Subject compliance will be defined in the Statistical Analysis Plan.

5.4. Prior and Concomitant Medications

Subjects will maintain their protocol-permitted standard of care throughout the study. All medications taken for the treatment of SLE/CLE will be recorded in the source documents and in the eCRF. All other medications (for non-SLE/CLE indications) taken up to 28 days prior to the screening visit through the end of the study (28 days after the last dose of study drug) must be recorded in the source documents and in the eCRF. At each study visit, the investigator site must capture any and all medications taken by the subject since the last visit or during the visit (as applicable). Concomitant medications include prescription and nonprescription medications, dietary supplements, vitamins, and minerals.

Currently effective therapies should not be discontinued for the sole purpose of participating in this study. Subjects may receive medications to treat AEs as deemed necessary by the investigator or the subject's health care provider(s). Should subjects have a need to initiate treatment with any prohibited concomitant medications, the sponsor medical monitor must be consulted prior to the initiation of the new medication, where possible. In instances where a prohibited medication is initiated prior to discussion with the sponsor, the investigator must notify the sponsor as soon as she/he is aware of the use of the excluded medication.

5.4.1. Allowed Concomitant Medications

Protocol-permitted medications taken for the treatment of CLE/SLE should be maintained, as much as possible, at stable doses (defined as no change in prescription) for the respective period of time specified below, prior to randomization through Week 4 (W4; [Table 5-1](#)).

For subjects that discontinue study treatment prior to Week 4, any modification to standard of care will be per investigator discretion.

The following medications should be maintained at stable doses for 60 days or greater (≥ 60 days) prior to randomization through Week 4:

- Nonbiologic immunosuppressive/immunomodulatory agents
 - Oral antimalarials (eg, hydroxychloroquine [≤ 400 mg/day], chloroquine [≤ 250 mg/day], quinacrine [≤ 100 mg/day], mepacrine [≤ 200 mg/day], dapsone [≤ 100 mg/day])
 - Oral or injectable MTX (up to 25 mg weekly); subjects on MTX should also be on folic acid supplementation (or equivalent), per local standard of care
 - Other csDMARDs, including azathioprine (≤ 2.5 mg/kg/day, not to exceed 200 mg/day), colchicine, cyclosporine, gold salts, leflunomide (≤ 20 mg/day), minocycline, mycophenolate mofetil (≤ 3 gm/day), mycophenolic acid (≤ 2.16 gm/day), penicillamine, sirolimus, sulfasalazine (≤ 3 gm/day), oral (not topical) tacrolimus

The following medications should be maintained at stable doses for 28 days or greater (≥ 28 days) prior to randomization through Week 4.

- Class V-VII topical corticosteroids; if the investigator wishes to use a Class V-VII topical corticosteroid not listed below, the investigator should obtain approval from the Gilead medical monitor prior to initiation of the medication, where possible
 - Alclometasone dipropionate up to 0.05% concentration
 - Desonide up to 0.05% concentration
 - Fluocinolone acetonide up to 0.03% concentration
 - Fluticasone propionate up to 0.05% concentration
 - Hydrocortisone acetate up to 2.5% concentration
 - Hydrocortisone probutate up to 0.1% concentration
 - Hydrocortisone valerate up to 0.2% concentration

- Oral prednisone \leq 15 mg/day (or equivalent)
- Vitamins, minerals, and herbal supplements (excluding prohibited herbal/natural supplements as listed in Table 5-3)
- Vaccines
 - Prior to study participation, it is recommended that the subject’s vaccinations be brought up to date according to local vaccination standards.
 - Inactivated vaccines (such as inactivated flu vaccines) should be administered according to local vaccination standards whenever medically appropriate; however, there are no available data on the concurrent use of GS-5718 and its impact on immune responses following vaccination
 - If possible, vaccination against SARS-CoV-2 should be concluded 28 days prior to randomization. Investigators must notify the medical monitor if/when a subject has received a SARS-CoV-2 vaccine within 28 days of randomization or until 28 days after the subject’s last dose of study drug.

Table 5-1. Allowed CLE/SLE Medications

Drug Class	Medication	Maintenance Period (Stable Dosing Prior to Randomization)
Nonbiologic Immunosuppressant/Immunomodulator ^a	Antimalarials (eg, hydroxychloroquine, chloroquine, quinacrine, mepacrine, dapsone), azathioprine, colchicine, cyclosporine, oral (not topical) tacrolimus, gold salts, leflunomide, minocycline, methotrexate ^b , mycophenolate mofetil, penicillamine, sirolimus, sulfasalazine ^b , or other immunomodulatory/immunosuppressive agent	Stable dosing must be maintained for \geq 60 days prior to randomization through W4
Corticosteroid, Local	Class V-VII topical corticosteroid	Stable dosing must be maintained for \geq 28 days prior to randomization through W4
Corticosteroid, Systemic	Oral prednisone \leq 15 mg/day (or equivalent)	Stable dosing must be maintained for \geq 28 days prior to randomization through W4

^a Refer to the dose limits specified in Section 5.4.1.

^b Methotrexate and sulfasalazine are BCRP substrates. GS-5718 may increase exposure of BCRP substrates. These medications are allowed but should be used with caution with GS-5718.

5.4.2. Prior and Concomitant Medications That Are Prohibited or To Be Used with Caution

Medications in [Table 5-2](#) and [Table 5-3](#) are prohibited or should be used with caution while participants are taking study drugs. The following medications are prohibited from concomitant use with study drug. The respective washout period (ie, prohibited period) relative to the date of randomization is specified below ([Table 5-3](#)).

For subjects that discontinue study drug prior to Week 4, initiation of any of these agents as standard of care will be per investigator discretion.

Prior exposure at any time to any medication in the following drug class is prohibited.

- IRAK4 inhibitors

Exposure to the following medications within 180 days (< 180 days) prior to randomization is prohibited.

- Biologic DMARDs (approved or unapproved)
 - Anti-TNF agents (eg, adalimumab, certolizumab, etanercept, infliximab, golimumab)
 - Non-TNF biologics (eg, anakinra, abatacept, sarilumab, tocilizumab)
 - Anti-B-cell activating factor (eg, belimumab), B-cell depleting agents (anti-CD20, eg, rituximab, ocrelizumab), or anti-CD22 agents (eg, epratuzumab); subjects with prior exposure to a B-cell depleting bDMARD (eg, rituximab, ocrelizumab), must have the presence of CD19⁺ B cells by flow cytometry at screening

Exposure to the following medication within 60 days (< 60 days) prior to randomization is prohibited.

- Cyclophosphamide
- JAK inhibitors (eg, tofacitinib, baricitinib, upadacitinib)

Exposure to the following medications within 28 days (< 28 days) prior to randomization is prohibited.

- Local corticosteroids
 - Intralesional or intraarticular corticosteroids
 - Class I-IV topical corticosteroids
- Systemic corticosteroids
 - Oral prednisone > 15 mg/day (or equivalent)
 - Intramuscular corticosteroids

- Topical calcineurin inhibitors (eg, tacrolimus, pimecrolimus)
- Any investigational drug, drug/device received or potentially received (within 28 days or 5 half-lives (whichever is longer))
- Live/attenuated vaccine (receipt of a live/attenuated vaccine within 28 days prior to randomization and until 28 days after the subject’s last dose of study drug)
 - Subjects should be advised to avoid routine household contact with persons vaccinated with live/attenuated vaccine components.

Exposure to the following medications within 14 days (< 14 days) prior to randomization is prohibited.

- Strong CYP3A inhibitors
- Strong CYP3A inducers

Table 5-2. Examples of Prior and Concomitant Medications That Are to Be Used With Caution or That Are Prohibited Because of the Potential for Pharmacokinetic Drug-Drug Interaction With GS-5718^a

Medication Class	Agents to Be Used With Caution ^b	Prohibited Agents ^c
Strong CYP3A Inhibitors	-	Cobicistat, ritonavir, ketoconazole, voriconazole, clarithromycin, itraconazole, grapefruit, grapefruit juice
Strong CYP3A Inducers	-	Phenytoin, carbamazepine, rifabutin, rifapentine, rifampin, St. John’s wort
BCRP Sensitive Substrates	Rosuvastatin (allowed for use but dose should not exceed 20 mg)	-
OCT2, MATE1, MATE2K Sensitive Substrate	Metformin (allowed for use but monitor blood glucose more frequently)	-

BCRP = breast cancer resistance protein; CYP3A = cytochrome P450 3A; MATE1 = multidrug and toxin extrusion 1; MATE2K = multidrug and toxin extrusion 2K; OCT2 = organic cation transporter abbreviation 2

a This table represents examples of the most common concomitant medications and is not meant to be exhaustive. Additional lists on potential perpetrators can be found at <https://drug-interactions.medicine.iu.edu/MainTable.aspx>. If the investigator is unsure if a medication is allowed per protocol, he/she should consult with the sponsor medical monitor.

b Agents should be used with caution < 3 days prior to Day 1 through Week 4

c < 14 days prior to Day 1 through Week 4

Table 5-3. Prohibited Medications

Drug Class	Medication	Prohibited Period (Relative to Randomization)
IRAK4 inhibitor		Prior exposure disallowed
Biologic	Tumor necrosis factor (TNF) inhibitor, non-TNF biologic (eg, anakinra, abatacept, belimumab, rituximab ^a , ocrelizumab ^a , tocilizumab, sarilumab), or biosimilar (if applicable)	< 180 days prior to randomization through W4
Cyclophosphamide		< 60 days prior to randomization through W4
JAK inhibitors (eg, tofacitinib, baricitinib, upadacitinib)		< 60 days prior to randomization through W4
Investigational	Any investigational drug, drug/device received or potentially received	< 28 days or 5 half-lives (whichever is longer) prior to randomization through W4
Live/attenuated vaccine (eg, intranasal flu, Zostavax, varicella, measles/mumps/rubella (MMR), yellow fever)		< 28 days prior to randomization and until 28 days after the last dose of study drug
Topical Calcineurin Inhibitors	Topical tacrolimus, topical pimecrolimus	< 28 days prior to randomization through W4
Corticosteroid, Local	Intralesional or intraarticular corticosteroid, Class I-IV topical corticosteroid	< 28 days prior to randomization through W4
Corticosteroid, Systemic	Oral prednisone > 15 mg/day (or equivalent), intramuscular corticosteroid	< 28 days prior to randomization through W4

bDMARD = biologic disease-modifying antirheumatic drug; IRAK4 = interleukin-1 receptor-associated kinase 4; JAK = janus kinase; W = Week

^a Subjects with prior exposure to a B-cell depleting bDMARD (eg, rituximab), must have the presence of CD19+ B cells by flow cytometry at screening

Consult the medical monitor for any herbal/natural supplements not listed that may have potential drug-drug interactions with study drug or if it is unknown whether there is a potential drug-drug interaction with study drug.

Subjects should be advised to avoid ultraviolet light exposure, utilize sunscreen, and wear protective clothing during the study and for 28 days after the subject's last dose of study drug.

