8.9. Sample Size

Sample size was determined based on practical considerations and no sample size calculation was performed. A sample size of 12 evaluable subjects (8 subjects randomized to GS-5718 and 4 subjects randomized to placebo) should provide a suitable assessment of the descriptive safety and PK profile.

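### Section 5.4.1 caps quinacrine at 100 mg/day and mepacrine at 200 mg/day; if these are one drug, a dose between the caps is both permitted and not permitted

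*Protocol*

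**What the plan says.** Protocol Section 5.4.1 names the oral antimalarials that subjects may continue and puts a daily maximum beside each. Two adjacent entries read "quinacrine [≤ 100 mg/day], mepacrine [≤ 200 mg/day". They appear as different agents, with no note connecting them.

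Table 5-1 in the same section carries both names again: "Antimalarials (eg, hydroxychloroquine, chloroquine, quinacrine, mepacrine, dapsone". The table gives no doses of its own. Its footnote a, attached to the whole drug class, says "Refer to the dose limits specified in Section 5.4.1".

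The limits reach eligibility through inclusion criterion 6 (Section 4.2 and the synopsis). It applies to "Subjects using protocol-permitted nonbiologic immunosuppressive/immunomodulatory agents for the treatment of CLE/SLE", requires a stable dose for at least 60 days before randomization and on through Week 4, and refers to Section 5.4.1 for details.

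Only one of the two names appears elsewhere. Criterion 8c, on prior intolerance or inadequate response, includes "chloroquine, quinacrine, hydroxychloroquine, azathioprine, MMF, leflunomide, dapsone, or MTX", without a dose and without mepacrine. The SAP does not mention either drug.

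**The concern.** A dose ceiling in a permitted-medication list has to give one answer for one drug at one dose. If quinacrine and mepacrine are the same substance, this list gives two. A site that records quinacrine reads the lower ceiling and a site that records mepacrine reads the higher one. Each sees a clear number and has no reason to query it.

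What is at stake is consistent application of criterion 6, and of the Section 5.4 rule that subjects stay on permitted standard of care. The study planned approximately 12 centers worldwide, and Section 5.2.2 provides for supply to the US and other countries, so different sites could use different names. The documents do not show that any did.

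**Working it through.** No sample size, power or variance figure enters this point. Section 8.9 states that "Sample size was determined based on practical considerations and no sample size calculation was performed". The check is a comparison of the passages.

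**Inputs**

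- Ceiling under the name quinacrine: 100 mg/day (Section 5.4.1).
- Ceiling under the name mepacrine: 200 mg/day (Section 5.4.1).
- Table 5-1: both names, no separate limits, footnote a deferring to Section 5.4.1.
- Criterion 6: permitted agents, stable for at least 60 days, details in Section 5.4.1.
- Assumption, not in the documents: the two names denote one substance.

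**Step 1: compare the ceilings.** 200 / 100 = 2, so the limits differ two-fold.

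**Step 2: apply both ceilings to the same daily dose.**

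| Stable daily dose | Recorded as quinacrine | Recorded as mepacrine | Consistent? |
|---|---|---|---|
| 100 mg or less | within limit | within limit | yes |
| above 100, up to 200 mg | over limit | within limit | no |
| above 200 mg | over limit | over limit | yes |

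Only the middle band is affected. At 150 mg/day, for example, the same subject is over the limit under one name and within it under the other.

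**Step 3: look for text that resolves it.** Table 5-1 repeats the names and sends the reader back to the same limits. Criterion 8c has no dose. The prohibited-medication lists in Section 5.4.2 and Tables 5-2 and 5-3 contain neither name. Nothing identifies the names as synonyms, explains the difference or says which entry governs.

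**Step 4: can the site adjust its way out?** Not within one screening period. Screening lasts at most 28 days before Day 1, and criterion 6 asks for at least 60 days of stable dosing. Since 28 < 60, a dose changed during screening cannot meet the stability rule by Day 1. Section 4.4 allows one rescreening with the medical monitor's approval, so later entry is conceivable.

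**The case against.** **The premise is outside the documents.** The protocol treats the two as different agents, and if they were, there would be no contradiction. This stands as a limit on certainty, so the identity is stated as an assumption. It is a matter of drug naming that the sponsor can confirm at once. Both conflicting figures are the protocol's own.

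**The list is only illustrative.** The antimalarials are given as examples, and Table 5-1 also allows other immunomodulatory or immunosuppressive agents. That widens which agents are allowed. It does not cancel a numerical limit attached to a named agent, and footnote a applies those limits to the class. Likewise, the softening phrase in Section 5.4.1 about keeping doses stable where possible concerns stability, not the ceilings.

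**Criterion 6 is worded as a stability rule.** It does not say in so many words that an over-limit dose excludes a subject. That is so, but the criterion relies on the idea of a permitted agent and points to Section 5.4.1 for it, and that is where the two ceilings conflict.

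Two stronger readings are tempting, and the documents support neither:

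- A reader might infer that the naming decides whether a subject is replaced under Section 4.1.1. That section lists use of prohibited medication or a change to background therapy. A stable dose above one of the ceilings is neither, since this drug is not on the prohibited lists, and replacement is discretionary.
- A reader might infer that the two ceilings introduce a material two-fold spread in background exposure. The ceilings do not standardize exposure in the first place. Several permitted agents (colchicine, cyclosporine, gold salts, minocycline, penicillamine, sirolimus, oral tacrolimus) have no numerical limit, and every stated limit is only a maximum. The control the design relies on is a stable dose, which the naming does not affect.

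**Conclusion.** The point holds as a contradictory threshold for permitted background therapy, conditional on the two names denoting one substance. Its reach is one drug, at doses above 100 and up to 200 mg/day, and it bears on eligibility and on which background therapy counts as permitted.

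The practical size is small. About 12 subjects were planned. SAP Section 1 reports that screening stopped with 3 enrolled and that the study was discontinued. The number of subjects who took this drug is not given and is probably small. The primary endpoints are descriptive counts of adverse events and laboratory abnormalities. The SAP uses no covariates or subgroups (Sections 3.3 and 3.4), and prior and concomitant medications are listed without being summarized (Section 7.4). No endpoint or analysis changes. With enrollment closed, the correction matters mainly if this medication list is reused.

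**What to change.** The sponsor should confirm that the two names refer to one substance. If they do, the two entries must be reconciled: name the substance once, as quinacrine/mepacrine, with a single limit in Section 5.4.1, and once in Table 5-1. Which figure is right is for the sponsor to settle. If the two are intended as different agents, Section 5.4.1 should say so. The cost is one line in Section 5.4.1 and one in Table 5-1, with no change to the SAP.
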